18 PROCESS EVALUATION

The process evaluation is presented in two parts: (1) the internal pilot, focusing on trial methods, specifically recruitment, as well as early engagement in and implementation of the intervention and (2) the main trial, which focusses on understanding of if and how physical activity, alongside other smoking reduction strategies, contributes to smoking reduction and cessation.

A mixed-methods embedded process evaluation will enable us to more fully understand how the respective components of the intervention are interacting and featuring if and when smokers do manage to reduce and quit smoking. It is important to understand not only if the intervention is effective but also whether there are some key and not so important components to improve more efficient training and delivery during any implementation phase. Equally, if the intervention is shown not to be effective then it is important to understand why and whether future intervention modifications are merited. Given the sparsity of rigorous research on behavioural approaches such as the one proposed for the target population it will be important to maximise what can be learnt. Further, it is vital, in the initial internal pilot phase, for the process evaluation to focus on understanding and refining the trial methods in order to maximise recruitment, and initial intervention engagement.

18.1 Internal pilot:

During the internal pilot phase (1-4 months of recruitment) the focus will be on feasibility and acceptability of trial methods and early understanding of aspects of intervention implementation including training and supervision, as well as early indications of intervention engagement, as follows:

18.1.1 Interviews with decliners:

To inform our understanding of recruitment feasibility and acceptability, participants who are eligible but who decline to join the study will be asked to indicate by return of the reply slip included in the TIP if they are willing to be contacted for a short telephone interview to determine what influenced their decision not to join the study. Questions will broadly focus on the following: (a) understanding of what the study/intervention is about based on the TIP materials; (b) barriers to taking part in the

study; (c) perceptions of materials contained in the TIP; (d) perceptions of what would influence them to take part in the study.

18.1.2 Interviews with study participants:

To further inform our understanding of the acceptability and feasibility of both recruitment and intervention we will interview (either in person or by phone) study participants from both the control group and intervention group. Questions will broadly focus on the following: (a) understanding of what the study/intervention is about based on the TIP materials; (b) motivation for taking part in the study; (c) perceptions of materials contained in the TIP; (d) perceptions of being informed of their allocation to the control group and intervention group (as applicable). Interviews with participants in the intervention group (both those who have engaged with the intervention and those who have not engaged with the intervention within 3 weeks of being informed of their allocation), will also inform our understanding of perceptions of engaging with the intervention. Questions will be based on issues including (a) initial engagement; (b) acceptability of core components of the intervention; (c) acceptability of materials; (d) use of other aids to self-regulate smoking.

We will seek to interview as many participants as possible at this stage but anticipate that decliners may also be not willing to be interviewed.

18.1.3 Interviews with Research Assistants:

Short telephone/Skype interviews will be conducted with Research Assistants (RAs) at each site in order to identify barriers and facilitators to recruitment. Interviews will be recorded and summary notes taken. RAs will be asked to keep a log of their recruitment observations to support their participation in regular interviews (approximately every 2-3 weeks in the pilot phase), the findings of which will be formatively fed back to each site in order to trouble shoot teething issues and maximise recruitment.

18.1.4 Interviews with Health Trainers:

Health Trainers (HTs) will be interviewed (via telephone/Skype/in person as appropriate) at key points both immediately prior to and during intervention delivery in the pilot phase. HTs will be interviewed at each site in order to inform our understanding of (a) perceptions of acceptability and utility of HT training and manual; (b) receipt of training objectives (training fidelity); (c) perceptions of supervision; (d) experience of participant allocation; (e) perceptions of experience of delivering the intervention delivery including both practical issues and delivery of core competencies. Issues raised will be fed formatively into supervision and training updates as appropriate.

18.1.5 Interviews with GPs/Practice managers:

In addition to notes kept by the Research Assistants, GP practice staff involved in pre-screening at each site will be invited to take part in short telephone interviews to inform our understanding of this process. Interviews will broadly focus on: (a) acceptability and feasibility of use of read codes used as proxy indicators for inclusion/exclusion criteria; (b) resource needed/burden on practices; (c) barriers and facilitators to effective pre-screening and working with the research team. Interviews will be conducted most intensely in the initial stages of screening and recruitment and findings used to enhance the acceptability and effectiveness of screening methods.

Due to a limited budget awarded for the process evaluation, although we will audio record all interviews conducted during the process evaluation during the internal pilot, not all interviews will be transcribed during the internal pilot. Where interviews are not fully transcribed, detailed notes will be kept and collated to inform decisions about progress to the full trial.

18.2 Main trial

We will use recorded data from focus groups (one per site) and semi-structured interviews with HTs (n=8) and participants (n=20). Participant interviews will be conducted either in person or via telephone, with participants purposively selected by site. Field notes from HT training and supervision, HT session contact notes, and from recorded intervention sessions will also form the data corpus. For the latter, intervention fidelity will be assessed using a coding system developed during the pilot study which appeared to be robust in its application for assessing the delivery of the key intervention processes [63]. Recorded sessions through the multiple sessions (3 sessions from 30 participants, i.e. 90 session recordings held between a single HT and participant will be assessed to ensure capture of variations in planned intervention content over time. Participants will be selected where recordings have been achieved at the start, middle and end of engagement, and will be purposively sampled by outcome (e.g. those who have made a quit attempt; reduced smoking) and demographic characteristics (e.g. age and gender). Health Trainer contact notes and records of contact number, type and duration will further inform the picture of intervention engagement.

The potential use of smoking reduction and cessation aids by participants in the TARS study is somewhat of an unknown, and will need to be assessed during initial intervention refinement (as above) and within the trial, particularly in terms of the impact on how physical activity plays a role in smoking reduction and possibly cessation. Also, with enhanced training of HTs they may be better equipped to support physical activity change as a way to aid smoking reduction and cessation (based on possible ways this could work identified above), but equally there may still be a proportion of smokers who find alternative approaches to reduction to be more acceptable. Semi structured interviews will be conducted with participants purposively sampled to cover a range of demographics and outcomes. It is intended to identify participants who have and have not engaged in physical activity, and those who have and have not reduced smoking to provide additional rich information about perceptions of delivery and receipt of the intervention. Key intervention components which facilitated intervention effectiveness (or not) will be analysed to complement other information in support of our logic model or not. Further, participants' understanding and experience of the intervention received will be explored (receipt fidelity). PPI groups will be consulted to help us understand this information and translate it into dissemination and implementation plans as appropriate.

18.3 Analysis

Qualitative data will be subject to thematic analysis using constant comparison techniques to extract concepts and themes [76] (and using NVivo to manage the data). The transcripts relating to smoker experiences of the intervention will also be analysed to produce a sample of individual narratives, allowing an increased insight into the processes of intervention engagement and the processes of supporting behaviour change [77]. Second coding of a sample of the transcripts and discussion of the emerging coding framework, as well as techniques such as negative case-finding and hypothesis testing will be used to increase the depth of analysis and enhance the likely objectivity of interpretation [79].

As reported in the section above on secondary outcomes, we will examine changes in smoking and physical activity and related beliefs, as well as information about intervention engagement. We will conduct exploratory mediation analysis to determine if changes between baseline and 3 months in items to assess behaviour change constructs (ie, perceived importance and confidence to change smoking and physical activity, availability of support, use of physical activity to aid changes in smoking, urges and strength of urges to smoke, and self-monitoring and engagement in planning to change smoking and physical activity) mediate changes in smoking and physical activity.

19 ECONOMIC EVALUATION (Cost-Effectiveness Analyses)

19.1 Health economic outcome measures

Health related quality of life (EQ-5D-5L)

The EQ-5D is a standardised measure of health status developed by the EuroQol Group in order to provide a simple, generic measure of health for clinical and economic appraisal (EuroQol Group, 1990). The EQ-5D-5L descriptive system comprises the following 5 dimensions: mobility, self-care, usual activities, pain/discomfort and anxiety/depression. Each dimension has 5 levels; no problems, slight problems, moderate problems, severe problems, and extreme problems (Herdman et al 2011 [69]). In this study participants will be asked to complete EQ-5D-5L as part of the questionnaire booklet mailed to them from CTU at baseline, and then at 3 months follow-up and 9 months follow-up.

Health service utilisation and costs (including smoking related costs)

A resource use questionnaire (RUQ) has been developed and used to collect self-report data from participants on key areas of health care resource use (e.g. GP contacts, hospital admission). The RUQ is based on previously used questionnaires of this type in a primary care research setting. Participants will be asked to complete this as part of the questionnaire booklets at baseline, 3 and 9 months. The booklet will be mailed to participants from CTU at 3 and 9 months.

19.2 Economic evaluation

An economic evaluation will be undertaken to estimate the cost-effectiveness of the intervention versus SAU, for smokers wishing to reduce but not quit smoking, alongside the RCT (trial-based analyses, over 9 month follow up) and over a longer term time horizon using a decision analytic model based framework. The primary perspective of the analyses will be that of the NHS and Personal Social Services (i.e. Third Party Payer), with a broader perspective explored in sensitivity analyses; results will be presented in a UK policy-relevant context. The primary economic endpoint will be the QALY, derived in trial-based analyses using the EQ-5D-5L, over the 9-month follow-up, with cost-effectiveness presented using incremental cost per QALY.

In the prior pilot study (EARS) methods of data collection on resource use associated with the delivery of the intervention were developed and tested. These methods will be used (including some adaptation where appropriate) in this full RCT and evaluation, to collect data on the delivery of the TARS intervention (HT time inputs for delivery of the intervention, and resources related to training and supervision of HTs, plus consumables). Data on time input for HTs (contact time, participant related non-contact time) will be collected within-trial using a HT 'contact sheet' completed by HTs for each contact with intervention participants. Data will be collected within-trial, via Trial Coordinator/s, on resource use for the training of HTs, and for ongoing specific supervision requirements for HTs, plus other related consumables and intervention expenses. A resource use questionnaire (RUQ) will be used to collect self-report participant data on use of health care services. As above, this RUQ will be completed at baseline, 3-month and 9-month follow-up assessments, and will be used to derive a profile of resource use at participant level over the 9-month follow-up. Items of resource use will be combined with published estimates of unit costs (e.g. NHS reference costs, data from PSSRU [66]), to estimate costs associated with broader service use by group.

The economic endpoint will be the QALY, and the EQ-5D-5L data from trial participants will be used to derive health state values at each time point, using the published tariff values for England (presently recommendations are for values to be derived using methods reported by Van Hout et al 2015 [81]). The EQ-5D-5L data will be used to derive participant level QALY data over the 9-month follow up, using the area under the curve approach (Brazier et al, 2007 [73]).

A trial-based cost-effectiveness analysis will present estimates of intervention cost, broader resource use costs, and QALYs, by group, and will estimate the incremental cost per unit of outcome (e.g. cost per incremental QALY) over the 9-month follow-up. Analyses will assess uncertainty, and will present sensitivity analyses. Analysis of cost data, for health care services will be undertaken using regression based analyses to estimate differences between groups over time, adjusting for baseline cost estimates, and other co variates specficied in the analyses of effectiveness, and through applying bootstrap methods to account for the non parametric nature of cost data. A similar regression based approach will be used to estimate differences in EQ-5D-5L values and derived QALYs between intervention and control participants.

In addition to the trial-based economic evaluation, a model-based economic evaluation will also be undertaken to estimate the cost effectiveness of the intervention versus SAU. This will adopt a longer term perspective (lifetime horizon/time-frame), beyond the trial follow, to present a policy relevant cost effectiveness analyses, consistent with the approach commonly applied in smoking cessation settings. A decision-analytic model will be used to deliver this model-based evaluation, and to allow the evidence synthesis required to perform this analysis. A decision analytic model was developed and used as part of the prior pilot study (EARS), and that model will be used as the basis for the model-based evaluation in the current TARS project. However, we will update the review of the literature (undertaken in the pilot study) and we will further develop and adapt the model developed where required and appropriate.

Building on our prior research on model development, we will update to previously reported review of the literature to identify new research on methods related to modelling cost effectiveness in a smoking cessation setting, and on important input parameters for a model based framework (e.g. relapse rate, mortality data). The starting point for modelling cost effectiveness is effectiveness (trial) data on abstinence rates (intervention vs SAU). Thereafter, through evidence synthesis, the model will predict smoking status over time and will be driven by estimates of mortality by smoking status. Using a Markov type model, with states for 'smoker', 'former smoker' and death, and a cohort simulation model structure (although other scenarios will be considered), aligned to age (e.g. decile age bands) and gender, we will estimate the number of long term guitters, the cost per life year saved, and cost per QALY gained. In the pilot study (EARS) we used an exponential survival function for remaining smoke free (time to event/relapse analyses), over an initial 7-year period of follow-up (beyond initial 12-months), consistent with evidence that the proportion of quitters follows a decreasing trend. Prior research did not include spontaneous quit rate beyond 8 years, but this will be explored in current (TARS) model development (e.g. using data from Coleman et al [67]). The TARS study will we expect allow development of a the model in terms of mortality by applying mortality rates dependent on time since quit to model the relation between sustained abstinence and smoking related mortality. Detail on this is presented in the pilot study report ([name] et al, 2014, Chapter 6 [1]). In prior research we have applied mortality data with data on health state values (QALY weights) by smoking status, available by age and gender [68]. TARS will build on prior research on the modelling of the impacts of smoking cessation strategies, to provide a rigorous presentation of estimates of the cost effectiveness of the intervention applied in the research proposed here. Methods will include cost analyses, literature review, evidence synthesis, trial-based cost effectiveness analyses (CEA), and longer term CEA using a decision-analytic modelling framework. The TARS study will apply methods of good practice in decision analytic modelling in a HTA context, and will explore uncertainty in assumptions and data inputs in a thorough and transparent way, including scenario analyses, one-way and multi-way sensitivity analyses and using probabilistic sensitivity analyses (alongside model based analyses).

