6 AIMS AND OBJECTIVE

The overarching research question is whether in addition to the usual standard support, a client-centred intervention with behavioural support to reduce smoking and promote physical activity, for smokers wishing to reduce smoking with no immediate plans to quit (but who may be open to the notion of quitting), can increase CO-confirmed prolonged abstinence at 9 months post baseline (i.e. 6 months post intervention) compared to standard support alone, and whether such an intervention is cost-effective.

The aims of the trial are as follows:

[figure not shown]
- To determine whether the additional behavioural support for an intervention promoting smoking reduction and increasing physical activity, compared to support as usual (SAU), significantly increases the proportion of participants who achieve prolonged abstinence at 9 months post baseline as confirmed by the concentrations of their expired CO.
- To determine whether the intervention, compared to SAU, increases the proportion of participants who reduce self-reported cigarette smoking by at least 50% at 3 and 9 months post baseline compared to baseline smoking levels, while quantifying the use of licenced nicotine containing products (LNCPs) and e-cigarettes.
- To determine whether the intervention, compared to SAU, increases the proportion of participants who achieve CO-confirmed prolonged abstinence at 15 months post baseline (i.e., 12 months post intervention).
- To determine whether the intervention, compared to SAU, increases self-reported physical activity at 3 and 9 months post baseline, and accelerometer assessed physical activity at 3 months post baseline.
- To determine whether the intervention, compared to SAU, improves quality of life (SF 12, EQ-5D-5L), weight and cigarette cravings at 3 and 9 months post baseline.
- To estimate the additional resource use and costs of delivering the intervention and to estimate
 the differences in health and social care service utilisation and the related costs between
 intervention and SAU at 9 months post baseline.

- To estimate the cost-effectiveness of the intervention compared with SAU at (i) 9 months (incremental cost per unit change in abstinence rate, and cost per quality adjusted life year [QALY] gained) and (ii) over a longer term / lifetime horizon (incremental cost per life year saved, per QALY gained) extrapolating beyond the trial using a previously developed decision-analytic model to estimate future costs and benefits.

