8.7 Baseline

Following receipt of informed consent study participants will be invited to complete baseline assessments. The baseline assessments will either be completed at a face-to-face screening/consent visit (as described above), or be mailed to participants in the form of a questionnaire booklet, with a cover letter, and freepost return envelope. If the booklet is mailed to the participant the opportunity will be given for participants to complete the questionnaire booklet over the telephone with a member of the local research team, if they would prefer. Randomisation will depend upon CTU receiving a completed baseline questionnaire booklet from the potential participant. A shopping voucher will be mailed to all participants upon CTU receipt of the completed baseline questionnaire booklet.

The baseline questionnaire booklet contains questions relating to the following:

- Smoking behaviour
- Importance and confidence in smoking reduction and cessation
- Importance and confidence in being physically active
- Availability of support to reduce smoking and increase physical activity
- Use of physical activity for smoking regulation
- Self-reported physical activity (7-day physical activity recall)
- Planning to change smoking
- Planning to change physical activity
- Self-monitoring of smoking
- Self-monitoring of physical activity
- Urges & strength of urge to smoke
- Use of e-cigarettes and NRT (nicotine replacement therapy) products
- Health related quality of life (EQ-5D-5L & SF12)
- Self-reported height and weight (BMI)
- · Health service utilisation and costs, including smoking related costs

Self-reported health & social care utilisation costs

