A shopping voucher will be mailed to all participants upon CTU receipt of the completed 3 month questionnaire booklet. No additional incentive will be provided for selected participants to return the accelerometer.

Expenses to attend the expired CO assessment session will also be provided.

10.2 9 month follow-up assessments

The 9 month assessments will be mailed to participants in the form of a questionnaire booklet, with a cover letter, and freepost return envelope. An opportunity will be given for participants to complete the questionnaire booklet over the telephone with a member of the local research team if they would prefer.

The 9 month questionnaire booklet contains questions relating to the following:

- Smoking behaviour
- Self-reported physical activity (7-day physical activity recall)
- Use of e-cigarettes and NRT (nicotine replacement therapy) products
- Health related quality of life (EQ-5D-5L & SF12)
- Self-reported height and weight (BMI)
- · Health service utilisation and costs, including smoking related costs
- · Serious adverse event reporting

Participants who self-report that they have quit will be invited to attend a face-to-face assessment which will include the following additional assessments:

- Self-reported prolonged abstinence (since last quit attempt, with date, if relevant)
- Expired carbon monoxide (CO) measurement

A shopping voucher will be mailed to participants upon CTU receipt of the completed 9 month questionnaire booklet.

Expenses to attend the expired CO assessment session will also be provided.

10.3 15 month follow-up assessments

The 15 month assessments will be mailed only to participants who are confirmed quitters at 9 months. The assessments will be in the form of a questionnaire booklet, with a cover letter, and freepost return envelope. An opportunity will be given for participants to complete the questionnaire booklet over the telephone with a member of the local research team if they would prefer.

The 15 month questionnaire booklet contains questions relating to the following:

- Smoking behaviour
- Use of e-cigarettes and NRT (nicotine replacement therapy) products

Only participants who have been confirmed as quitters at 9 months and self-reported quitting at 15 months will be invited to participate in the following 15 month assessments:

- Self-reported prolonged abstinence (since last quit attempt, with date, if relevant)
- Expired carbon monoxide (CO) measurement

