10.6 Schedule of delivery

	Screening &	Day	Intervention	Month	Month	Month
	Baseline	0	Week 1 – 8*	3	9	15
			(Intervention			
			arm only)			
Eligibility check	Х					
Consent	Х					
Randomisation		Х				
Demographics	Х					
Importance and confidence in smoking reduction and	Х			Х		
cessation						
Importance and confidence in being physically active	Х			Х		
Availability of support to reduce smoking and increase	Х			Х		
physical activity						
Use of physical activity for smoking regulation	Х			Х		
Self-reported physical activity (7-day physical activity	Х			Х	Х	
recall)						
Planning to change smoking	Х			Х		
Planning to change physical activity	Х			Х		
Self-monitoring of smoking	Х			Х		
Self-monitoring of physical activity	Х			Х		
Urge & strength of urge to smoke	Х			Х		
Use of e-cigarettes and NTR (nicotine replacement	Х			Х	Х	Х
therapy) products						
Health related quality of life (EQ-5D-5L & SF12)	Х			Х	Х	
Self-reported weight & height (BMI)	Х			Х	Х	
Health service utilisation and costs,	Х			Х	Х	
Serious adverse events (self-reported)				Х	Х	
Self-reported prolonged abstinence (since quit attempt,				Х	Х	Х
with date, if relevant)						
CO expired air confirmed abstinence (<10ppm)**				Х	Х	Х
Accelerometer (7 days)				Х		

^{*}If a smoker wishes to quit at any time during the 8 week intervention period, they will be offered 6 weeks of additional support from the Health Trainer, a meeting with a specialist advisor in a stop smoking service, and pharmacological and behavioural support.

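### The protocol names social care in a 9-month objective and in the primary cost perspective, but as written does not provide for collecting it at 3 and 9 months

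*Protocol*

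**What the plan says.** Two places commit the trial to social care. One aim in Protocol section 6 is to estimate "the differences in health and social care service utilisation and the related costs between" the arms, with the time point given as "intervention and SAU at 9 months post baseline". In section 19.2, "The primary perspective of the analyses will be that of the NHS and Personal Social Services"; a broader perspective is left to sensitivity analyses. Social care is therefore inside the primary cost analysis.

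The data-collection sections are narrower. The baseline booklet list (8.7) has a line on health service use and, after it, a separate line: "Self-reported health & social care utilisation costs". The 3-month list (10.1) and the 9-month list (10.2) carry only "Health service utilisation and costs, including smoking related costs". The schedule of delivery (10.6) has a single row, "Health service utilisation and costs", marked at baseline, month 3 and month 9. The outcome list (7.5) also names health services only.

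The economic sections follow the narrower wording. Section 19.1 describes the resource use questionnaire (RUQ) as covering health care, with GP contacts and hospital admission as examples. Section 19.2 says: "A resource use questionnaire (RUQ) will be used to collect self-report participant data on use of health care services". The cost regression in 19.2, which adjusts for baseline cost, is specified for health care services. Both 19.1 and 19.2 state that the RUQ is completed at baseline, 3 months and 9 months.

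**The concern.** An objective on social care at 9 months needs social care use to be recorded after randomisation in both arms. The protocol lists it once, before randomisation, and then describes follow-up and analysis in terms that leave it out.

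If the trial is run to that text, three things follow. The social care half of the section 6 objective has no follow-up data. The primary incremental cost per QALY is labelled NHS and Personal Social Services but contains no participant social care use after randomisation. The baseline social care item has no follow-up counterpart, so it cannot do its job in a regression that adjusts for baseline cost.

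This cannot be left to an analysis plan. What each booklet asks is fixed when it is mailed, section 16.6 says questionnaire data will not be queried with participants, and a recall period that has passed cannot be reliably rebuilt.

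**Working it through.** No arithmetic applies: the point concerns which items are listed at which visit. The relevant places are set side by side below.

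| Protocol section | Role | Health services | Social care |
|---|---|---|---|
| 6 | Objective at 9 months | Yes | Yes |
| 19.2 | Primary perspective | Yes (NHS) | Yes (Personal Social Services) |
| 8.7 | Baseline booklet | Yes | Yes, on a separate line |
| 7.5 | Outcome list | Yes | No |
| 10.1 | 3-month booklet | Yes | No |
| 10.2 | 9-month booklet | Yes | No |
| 10.6 | Schedule | Yes, at baseline, 3 and 9 months | No row at any visit |
| 19.1 | RUQ description | Yes | No |
| 19.2 | RUQ purpose | Yes | No |
| 19.2 | Cost regression | Yes | No |

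1. Social care is in the objective, the perspective and one data list, the baseline one. It is in 0 of the 2 follow-up lists that cover resource use. The 15-month booklet (10.3) does not collect resource use and is not counted.

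2. The health service line is the same in 8.7, 10.1 and 10.2. The social care line stands in 8.7 and is absent from the other two. Because 8.7 lists it apart from the health service line, the health service label cannot simply be assumed to include it.

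3. The schedule is weaker evidence. It has no social care row even at baseline, so it conflicts with 8.7 as well and does not by itself show a gap between baseline and follow-up.

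4. The examples in 19.1 are open-ended, but they illustrate health care use. An open list of health care examples does not extend to social care.

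5. Section 19.2 also speaks of costing broader service use. In context that phrase separates participants' use of services from the cost of delivering the intervention. The only participant-level source named for service use is the RUQ, described there as covering health care.

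6. Sections 19.1 and 19.2 nonetheless describe one RUQ used at three time points, and no section describes a different baseline version. If the baseline social care items sit inside the RUQ, the same form would carry them to 3 and 9 months.

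Steps 1, 2, 4 and 5 show that no text provides for social care at follow-up. Step 6 shows that the text does not exclude it either.

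**The case against.** The strongest reply is that one instrument is described, repeated unchanged at baseline, 3 and 9 months, and that short labels in a protocol are not item lists. On this view the baseline social care line may be a reworded duplicate of the line before it, or a drafting leftover, and the schedule supports that because it treats baseline and follow-up alike. The unit-cost source cited in 19.2 covers health and social care by its title, which is compatible with an intention to cost both. The exclusion in 8.5 of people unable to walk unaided for 15 minutes suggests that social care use may be low.

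Much of this stands. The booklets are not in the document. A reader might infer that the social care cost difference cannot be estimated, or that all post-randomisation social care data will be missing. The documents do not support either statement, because the repeated RUQ may contain the items under a health service heading.

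It does not remove the inconsistency. If the items are in the RUQ, then 7.5, 10.1, 10.2, 10.6, 19.1 and the later parts of 19.2 describe it too narrowly, and the cost regression as specified leaves those costs out. If the baseline line is a leftover, the objective and the Personal Social Services part of the perspective have no data item at any visit. A wide-ranging unit-cost source supplies prices, not quantities of use. Low expected use bears on the size of the effect, not on whether a stated objective has data behind it.

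**Conclusion.** The point holds as an internal inconsistency. The protocol commits to social care in a 9-month objective and in its primary cost perspective, and as written does not provide for that use to be collected at 3 and 9 months or included in the cost regression. That the data will actually be absent is not shown; it depends on booklets that are not in the document.

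Its reach is limited. The primary abstinence outcome, intervention costs, health care costs and QALYs are unaffected. What is exposed is the social care half of one objective and the Personal Social Services component of the primary cost per QALY. The size in money cannot be stated: the protocol gives no figure for social care use or cost, and none is assumed here. The inconsistency should be settled before the 3-month booklets are mailed, because the loss, if there is one, could not be made good at analysis.

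**What to change.** First, confirm whether the RUQ carries social care items at 3 and 9 months, and say so in section 19.1.

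- **If it does:** align 7.5, 10.1, 10.2, 10.6, 19.1 and 19.2 with sections 6 and 8.7, and widen the cost regression in 19.2 to include social care costs. This costs only an edit to the text.
- **If it does not, and social care is to stay in scope:** repeat the baseline social care items in the 3- and 9-month booklets, list them in 10.1, 10.2 and 10.6, and cost them in 19.2. The downside is a slightly longer mailed questionnaire at two time points.
- **If it does not, and social care is to be dropped:** restate the section 6 objective and the 19.2 primary perspective as NHS costs only, and remove the social care line from 8.7. This adds no burden for participants, but the primary cost perspective becomes narrower.
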